#### 7.2.3 Mortality

Deaths were recorded for each group.

## 7.3. Security indicators

General data: physical examination

Laboratory examination: Routine blood examination (including erythrocyte count, leukocyte count, hemoglobin, platelet count, proportion of monocytes, lymphocytes and neutrophils), urine routine (erythrocyte, leukocyte, urine protein), liver and kidney function (including ALT, AST, TBIL, BUN, Cr).

Symptoms accompanying any discomfort were recorded by the investigator

a) No: No symptoms

- b) Mild: Weak symptoms sometimes appeared
- c) Moderate: persistent but not noticeable after distraction
- d) Severe: Persisting no matter when

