#### **7.4. Follow-up examination**

The first examination was performed on the day of study start (D0). Follow-up was conducted every 7 days (i.e. D7, D14, D21, and D28) for all clinical examinations, all indicators of the trial, and routine laboratory examinations.

Side effect should be recorded during routine daily clinical examinations. If any side effect was found, follow up immediately and informed the researcher.

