##### **7.4.1. When the test started**

Signed informed consent.

Inclusion criteria and exclusion criteria.

Medical history was collected and the status of medication was inquired.

Routine physical examination.

Routine laboratory tests: Routine blood examination (including erythrocyte count, leukocyte count, hemoglobin, platelet count, proportion of monocytes, lymphocytes and neutrophils), urine routine (erythrocyte, leukocyte, urine protein), liver and kidney function (including ALT, AST, TBIL, BUN, CR), pregnancy test (women of child-bearing age), and other laboratory examination.

Combination medication was recorded.

Assigned random numbers.

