#### 10.2.4. Statistical expression

The results of repeated measurements were presented in tabular form with statistical graphs in order to easy read.

In general statistical tests, bilateral tests were used. If P was less than or equal to 0.05, it would be considered that the discriminant of the test was statistical significance.

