#### 10.2.6. Contents of statistical analysis

The statistical analysis plan was written by the statistician, finalized before the database lock, and consisted of a variety of tables. The main contents of the analysis included:

Case distribution: different data sets in each group, case distribution in each center, comparison of total abscission rate, and detailed list of termination causes.

Comparability analysis: compared demographic data with other base-value indicators to measure the comparability of the two groups.

Effectiveness analysis:  $X^2$  test and t test were used for main indicators and global indicators. Since this study was a multi-center clinical trial, central effect on the efficacy indicators should be considered in the analysis.

Analysis of the factors affecting the efficacy: such as age, sex, disease type, disease condition and so on, there were significant differences between the two groups before the use of vaccine, or if there were significant related factors that affected the vaccine effect, these factors should be used as co-factors when comparing the vaccine effect between the two groups for variables,

---

covariance analysis or Logistic regression analysis was required. The combination of medication and so on needed a detailed list.

Safety analysis: firstly, according to the requirements of side effect correlation, the side effect and adverse reactions of the two groups were listed and described (including the number of cases of various side effects, the number of cases and the conversion rate of "normal to abnormal" or "abnormal intensification" of laboratory test indicators before and after the test), and the reasons and explanations were listed.

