## 11. Quality control and assurance

### 11.1. Quality control

During the study, clinical inspectors will be commissioned by the sponsor to visit each study center regularly to ensure that all the contents of the study plan were strictly followed and the study data were filled in correctly.

The whole clinical trial process strictly followed the provisions of the national GCP (Good Clinical Practice) and conformed to the ethical principles. Participants might strictly abide by the standard operating procedures of clinical trial study.

Participants in clinical trials should be relatively fixed, and participants might undergo uniform training and had uniform recording methods and judgment criteria.

The researcher should fill in the CRF truthfully, carefully and use pen or carbon pen.

All observations and findings in clinical trials should be verified to ensure the reliability of the data and to ensure that the conclusions of clinical trials were derived from the original data. There were corresponding data management measures in clinical trial and data processing stage.

Medical records and medical record forms were regarded as the original records and generally could not be changed. When making any corrections, the original record should not be altered. Additional statement could be used to explain the reason, and then signed and dated by the physician participating in the clinical trial.

The researchers should take active measures (notice further consultation, follow up) to control the shedding rate within 20%.

Subjects would record their vaccination status on a diary card.

Each center should submit its normal range and abnormal judgment criteria to the responsible unit of clinical trial and the clinical statistical unit to ensure the accuracy, reliability and abnormal judgment criteria of laboratory examination.

All laboratory data should be recorded in the original medical record and the results of the tests should be glued to the original medical record. Laboratory data within the normal range should also be recorded in the CRF, and data that were significantly higher or outside the clinically acceptable range should be verified by the physician participating in the clinical trial to make the necessary statements.

Administration of vaccines:

Preservation conditions of experimental vaccine: under 23° C, sealed in a dark place.

---

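### White-cell differential safety indicators are named only as proportions; deriving absolute counts from data already recorded would give cleaner conversion tables (cheap improvement, minor in weight)

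*Combined protocol and SAP*

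**What the plan says.** Section 7.3 describes the routine blood examination as including the leukocyte count and, for the differential, the "proportion of monocytes, lymphocytes and neutrophils". Section 7.4.1 gives the same panel at study start, and section 7.4 repeats all indicators and routine laboratory tests at D7, D14, D21 and D28.

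The safety analysis in section 10.2.6 is descriptive. It reports the number and rate of subjects who go from normal to abnormal, or whose abnormality worsens, "of laboratory test indicators before and after the test". The limits come from the sites. Section 11.1 says "Each center should submit its normal range and abnormal judgment criteria", and gives no figures.

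Absolute neutrophil, lymphocyte and monocyte counts are not named, derived or assigned to an analysis anywhere. They are not excluded either. Section 10.2.6 also refers to a statistical analysis plan, made up of tables, to be finalized before database lock.

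**The concern.** The three proportions nearly fill one total, so they cannot move independently. If neutrophils rise and nothing else changes, the lymphocyte and monocyte proportions must fall, and a table built indicator by indicator can record an abnormality in a cell line that did not change. If lymphocytes alone fall, their denominator falls too. The proportion then moves less than the count, and the neutrophil proportion rises although neutrophils are unchanged.

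What is at stake is whether the laboratory safety table points to the right cell line and how readily it shows an isolated lymphocyte fall. Section 4.1 describes one arm, so there may be no concurrent group against which such artefacts could be recognized.

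**Working it through.** The documents state no figure to reproduce. The identity below is exact; every cell value is an assumption.

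**1. Identity.** With N, L, M and O the neutrophil, lymphocyte, monocyte and other counts, W = N + L + M + O and the lymphocyte proportion is L/W. Hence L = W x proportion. Both terms are in the same planned panel.

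**2. Hand example.** L stays at 1.8 while W rises from 6.0 to 7.8 through neutrophils alone. The proportion goes from 1.8/6.0 = 30% to 1.8/7.8 = 23%.

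**3. Two different events, one reading.** Assume N 3.8, L 2.0, M 0.45, O 0.2 (10^9/L), so W = 6.45 and the lymphocyte proportion is 2.0/6.45 = 31.0%.
- Neutrophils +50%: W = 8.35, proportion 2.0/8.35 = 24.0%, L still 2.0.
- Lymphocytes -30%: W = 5.85, proportion 1.4/5.85 = 23.9%, L now 1.4.

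The lymphocyte proportion alone cannot separate these; the absolute count does.

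**4. Size.** I simulated 400,000 subjects with lognormal counts and the medians in step 3. Between-subject CVs for N/L/M were 30/27/28% (A) or 35/25/30% (B). Within-subject CVs were 10% for N and L (A), or 20% for N and 12% for L (B), with 15% for M in both. Limits were the central 95% of baseline. The outcome was conversion at one visit among subjects normal at baseline. Entries are % of subjects, A / B.

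| True change | Low lymphocytes, proportion | Low lymphocytes, absolute | Ratio | Low leukocyte count |
|---|---|---|---|---|
| None | 1.2 / 1.6 | 1.2 / 1.5 | 0.97 / 1.11 | 1.2 / 1.6 |
| N +50% | 13.1 / 11.1 | 1.2 / 1.5 | all spurious | 0.0 / 0.1 |
| L -20% | 6.3 / 5.8 | 10.2 / 11.1 | 0.62 / 0.53 | 3.8 / 4.3 |
| L -30% | 12.9 / 10.8 | 22.8 / 24.4 | 0.56 / 0.44 | 6.3 / 6.5 |
| L -40% | 24.3 / 19.6 | 43.3 / 46.2 | 0.56 / 0.42 | 9.8 / 9.5 |
| L -50% | 42.0 / 34.0 | 69.6 / 72.9 | 0.60 / 0.47 | 14.4 / 13.4 |
| L -30%, N -15% | 6.1 / 5.5 | 22.8 / 24.4 | 0.27 / 0.23 | 15.9 / 13.4 |
| L -30%, N -30% | 1.8 / 2.1 | 22.8 / 24.5 | 0.08 / 0.09 | 34.3 / 26.2 |
| L -50%, N -50% | 3.1 / 3.0 | 69.6 / 73.0 | 0.04 / 0.04 | 87.2 / 73.7 |
| L -30%, N +30% | 31.1 / 25.1 | 22.8 / 24.6 | 1.37 / 1.02 | 0.6 / 1.4 |

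Other spurious flags: after N +50%, the monocyte proportion is low in 9.4 / 8.2%, against 1.6 / 1.5% by count. After L -30%, the neutrophil proportion is high in 7.5 / 6.5%, against 1.1 / 1.6% by count.

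**5. Check by hand (A).** The lower limits were 17.1% for the proportion and 1.148 for the count. With the other cells fixed at 4.45, the proportion reaches 17.1% when L = 0.171 x 4.45 / 0.829 = 0.918, a fall of 54% from 2.0. The count reaches its limit at a fall of 1 - 1.148/2.0 = 43%. For neutrophils alone to take the same adult to 17.1%, N must reach 2.0/0.171 - 2.65 = 9.05, or 2.38 times 3.8. The spurious flags after a 50% rise therefore come mainly from subjects who start nearer the limit.

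**6. Does the leukocyte count make up the loss?** Add its flags to those of the proportion as if they never overlapped. For L -40%, A gives 24.3 + 9.8 = 34.1 against 43.3, and B gives 19.6 + 9.5 = 29.1 against 46.2. For L -20% the gap almost closes: 10.1 against 10.2 (A) and 10.1 against 11.1 (B).

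**The case against.** **The leukocyte count is itself an indicator.** This stands for a general fall. When lymphocytes and neutrophils fall together by 30% or 50%, a low leukocyte count is at least as frequent as a low absolute lymphocyte count. A reader might infer that a fall in all cell types would go unseen; the planned panel does not support that. The leukocyte count does not make up the loss for a sizeable isolated lymphocyte fall (step 6).

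**Proportions are sometimes the more sensitive variable.** This stands. When neutrophils rise as lymphocytes fall, the proportion flags as many subjects or more. It is a reason to keep the proportions in the tables rather than move them to listings.

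**Absolute counts are not ruled out.** The panel is introduced as an open list, section 7.4.1 also allows for other laboratory tests, and tables can still be specified before database lock. So this is an unspecified derivation rather than missing data. But a plan that names proportions and tabulates conversions of its named indicators will produce proportion tables by default.

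**The harm is limited.** Section 10.2.6 lists conversions with reasons and explanations, and section 11.1 has a physician verify out-of-range results. No test, threshold or stopping rule rests on a lymphocyte proportion. Case review may catch a spurious flag, but it does not prompt anyone to look at a subject whose proportion stayed within limits.

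**Conclusion.** The point holds as a cheap improvement of minor weight. With proportions alone, the conversion tables can flag a cell line that did not change, and they under-detect an isolated lymphocyte fall: the ratio to the absolute count is about 0.4 to 0.6 under the two assumed sets of values.

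A reader might infer that the plan halves detection of lymphocyte falls. The documents do not support that as a general statement. They give no cell values, variability or limits, and the ratio runs from 0.04 to 1.37 with what neutrophils do. Nor is the size independent of the limits, since only central-95% limits were simulated. A reader might also take white-cell change to be the main safety signal for this product. Section 7.2.2 names fever, chills, coagulation dysfunction, allergy and disability, and the documents do not rank white-cell change above these.

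The point matters less than the absence of a sample size and the conflict between the one-arm design in section 4.1 and the two-group comparison in sections 10.2.3 and 10.2.6.

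**What to change.** In section 10.2.6, and in the statistical analysis plan finalized before database lock, derive absolute neutrophil, lymphocyte and monocyte counts as leukocyte count x proportion from the same sample at D0, D7, D14, D21 and D28. Make these the primary variables for the white-cell conversion tables, with absolute-count limits submitted by each center under section 11.1. Keep the three proportions as supportive tables beside them, and keep the leukocyte count as its own indicator. The panels in sections 7.3 and 7.4.1 need no new measurement.

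The cost is three derived variables and one added request for reference limits. No extra blood or visits are needed.

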#### **7.4. Follow-up examination**

The first examination was performed on the day of study start (D0). Follow-up was conducted every 7 days (i.e. D7, D14, D21, and D28) for all clinical examinations, all indicators of the trial, and routine laboratory examinations.

Side effect should be recorded during routine daily clinical examinations. If any side effect was found, follow up immediately and informed the researcher.

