## 4. Overall design and arrangement of the test

### 4.1. Test design

This study adopted a one-arm experimental design. The whole study mainly collected qualified normal healthy people without disease from the hospital, and excluded people with basic diseases such as hypertension, diabetes, hyperlipidemia and so on. Once confirmed, they were assigned to administer 1 dose of Bacillus subtilis spore. Follow-up observation and efficacy examination were performed on days 7, 14, 21 and 28.

If subjects had significant laboratory abnormalities or side effect at the end of the study, they should be followed up to normal.

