## 5. Subject selection

### 5.1. Inclusion criteria

Outpatient service (medical records of outpatient service shall be established), male or female, from 18 years old to 60 years old;

No hypertension, diabetes, hyperlipidemia and other basic diseases;

If the patient was a woman of gestational age, the pregnancy test at the time of screening should be negative; Contraception (oral or injectable contraceptives) should be used throughout the trial;

Obtained the informed written consent of the subject or the subject's immediate family member or the subject's guardian;

There was no serious cardiopulmonary liver and kidney insufficiency.

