#### 7.2.2 Safety of vaccines

Observed whether mild to moderate symptoms such as fever and chills appeared after taking the vaccine;

Observed whether there were severe symptoms such as coagulation dysfunction and allergy after taking the vaccine;

Observed whether there were serious symptoms such as disability after taking the vaccine.

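### Side effects are to be recorded at daily examinations that the weekly outpatient schedule does not contain, so symptoms that come and go between visits are likely to be under-recorded

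*Combined protocol and SAP*

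**What the plan says.** All references are to the combined protocol and SAP.

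- **Capture rule, section 7.4:** "Side effect should be recorded during routine daily clinical examinations". Any side effect that is found is then to be followed up at once and the researcher informed.
- **Visit schedule, section 7.4:** a first examination on D0, then "Follow-up was conducted every 7 days (i.e. D7, D14, D21, and D28) for all clinical examinations". Section 4.1 gives the same follow-up days: "Follow-up observation and efficacy examination were performed on days 7, 14, 21 and 28".
- **Setting, section 5.1:** "Outpatient service (medical records of outpatient service shall be established".
- **Subject-completed record, section 11.1:** "Subjects would record their vaccination status on a diary card".
- **Who records symptoms, section 7.3:** "Symptoms accompanying any discomfort were recorded by the investigator".
- **Named safety outcome, section 7.2.2:** "Observed whether mild to moderate symptoms such as fever and chills appeared after taking the vaccine".
- **Reporting window, section 8.1:** a side effect is any adverse medical event from consent and enrolment to the last follow-up, whatever its cause.

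**The concern.** The rule for collecting side effects relies on an examination that is not in the schedule. Nothing else in the plan supplies daily contact: there is no daily visit, telephone call, inpatient stay, post-dose observation period, temperature log or symptom diary. Fever and chills are named safety outcomes, and they can begin and end within a week. For an episode that does so, the plan gives no prospective way to record it.

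Three parts of the plan need better data than this:

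- The side-effect counts in section 10.2.6 fall directly if events are missed.
- The symptom scale in section 7.3 grades by persistence. Once a symptom has resolved, persistence can be judged only from memory.
- The causality table in section 8.3 uses the timing of onset and disappearance after stopping. Both need dates.

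Symptoms not recorded during the trial cannot be recovered at analysis.

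**Working it through.** The plan states no side-effect rate, symptom duration or reporting probability, so there is no figure of its own to reproduce. The check is a comparison of the text and a count of days.

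**1. Can the capture rule be carried out?** Section 7.4 ties all clinical examinations to D0 and the 7-day visits, and section 4.1 repeats the follow-up days. Section 5.1 makes the subjects outpatients. The daily examinations therefore have no schedule behind them.

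**2. Is there another route?** The investigator records symptoms (7.3), and the scheduled contacts with subjects are weekly. The diary card is described for vaccination status, and no symptom or temperature field is mentioned anywhere. Section 8.1 makes events between visits reportable but does not say how they are to be collected. What is left is recall at the next visit or spontaneous report.

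**3. Days with and without an examination.** D0 to D28 is 29 days, of which 5 have an examination. 29 − 5 = 24 days have none, and 24/29 = 83%.

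**4. Chance that a symptom is present on a visit day (illustration).** Assume onset is equally likely on each of D1 to D28 and the symptom lasts *d* whole days, with *d* = 1, 2 or 3. It is present at a visit on day *v* if onset falls on one of the *d* days from *v* − *d* + 1 to *v*. With four follow-up visits, 4*d* of the 28 onset days qualify.

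| Duration *d* | Onset days that overlap a visit | Share of 28 |
|---|---|---|
| 1 day | 4 | 14% |
| 2 days | 8 | 29% |
| 3 days | 12 | 43% |

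**5. Early onset.** A symptom that starts on D3 and lasts 3 days ends on D5, before the D7 visit. So no symptom of 1 to 3 days with onset on D0 to D3 is still present at D7. Unless it is seen at the D0 examination itself, it depends on recall or spontaneous report.

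**6. What under-reporting would do (illustration).** Recorded rate = true rate × probability that an episode is reported. Both inputs are assumed. With a true rate of 20%:

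| Assumed reporting probability | Recorded rate |
|---|---|
| 50% | 0.20 × 0.50 = 10% |
| 75% | 0.20 × 0.75 = 15% |
| 90% | 0.20 × 0.90 = 18% |
| 100% | 0.20 × 1.00 = 20% |

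The documents do not say where in this range the trial would fall.

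**The case against.** The strongest reply is that nothing limits recording to symptoms present at a visit. Section 8.1 counts any event up to the last follow-up, a subject can report at the next visit at most 7 days later, and section 7.4 requires immediate follow-up once an effect is found. This stands, and it rules out two inferences a reader might draw. One is that under-counting is certain. The other is that the complements of the overlap figures (86%, 71% and 57%) are the share of events lost. The overlap figures also rest on uniform onset, which may not fit reactions that cluster soon after a dose.

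A second reply is that the word for daily may be a translation of day-to-day. That is possible. Capture would then rest on the weekly visits alone, so the gap remains and the sentence still needs correcting.

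A third reply concerns the diary card. The text does not say that it is completed daily, so it should not be called an existing daily instrument. Nor does silence prove that it has no symptom fields. If such fields are intended, stating them is part of the fix.

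Finally, safety does not rest on fever and chills alone. The plan also covers severe symptoms, disability, deaths, and physical and laboratory examinations. The point is therefore confined to mild and moderate symptoms that fall between visits.

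**Conclusion.** The point holds in this limited form. The capture rule in section 7.4 contradicts the visit schedule in the same section and cannot be carried out as written. Mild to moderate symptoms between visits depend on recall or spontaneous report, and under-recording is likely. That last step is an inference: it assumes that some short episodes are forgotten or not mentioned.

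The size of the loss cannot be estimated from the documents. What can be stated is that 24 of 29 days have no examination, and that under the assumed uniform onset a symptom of 1 to 3 days coincides with a visit 14% to 43% of the time.

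The days on which reactions could arise also depend on an unresolved conflict: section 4.2 describes a single administration, while section 3 of the Summary and section 6.3 describe daily dosing. Those passages must be reconciled. Neither reading creates a daily examination, so the conclusion does not change.

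**What to change.** Before enrolment:

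1. **Section 7.4:** replace the sentence on daily examinations with subject self-recording, reviewed at each weekly visit. State that staff also ask at each visit about events since the last one.
2. **Section 11.1:** extend the diary card to daily temperature and a short list of solicited symptoms, for example fever, chills, gastrointestinal and allergic symptoms.
3. **Severity:** state which scale applies to the solicited symptoms. Section 7.3 grades by persistence and section 8.2 by effect on daily life, so the two can give different grades.
4. **Period:** run the diary to D28, or set the period once the dosing passages in section 4.2, section 6.3 and section 3 of the Summary have been reconciled.
5. **Section 10.2:** report the share of subjects with each solicited symptom, with an exact 95% confidence interval. Section 10.2.2 already lists frequencies and confidence intervals, so the additions are the solicited-symptom table and the exact method.

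Scripted questioning at each visit or telephone contacts would also give the plan a workable rule. The diary is preferable because it records symptoms by date without relying on a week's recall.

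**Cost:** no extra visits, but a daily task for subjects and more data to enter. Temperature plus the four example symptoms is 5 items a day. That is 5 × 8 = 40 entries per subject for D0 to D7, or 5 × 29 = 145 for D0 to D28, all subject to the double entry required by section 9.2.
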